**Assessments**

The assessment timelines are described in Table 3.

**Table 3:** Study design and assessments

Assessment	Baseline	Pre-CAT	finCAT	Post-CAT	Follow-Up
Demographics	X				
CIRS	X	X		X	X
GAS		X		X	X
LSP	X	X		X	X
EPBAS	X				X
Essen CES	X				X
Attitudes					X

**Study Model**

**Study Overview** (finCAT = Forensic Inpatient Cognitive Adaptation Training)

WEEK	0	1	2	3	4	5	6	7	8	9	10	11	12	13	14	15	16	17	18	19	20	21	22		
LGUC (n=6)	Base	Pre	finCAT				Post	Champion Follow-Up							Follow-Up									Provider Focus Group & Client Interview	
LGUA (n=6)	Base	Pre	finCAT				Post	Champion Follow-Up							Follow-Up										Provider Focus Group & Client Interview
LGUB (n=6)	Base					Pre	finCAT			Post	Champion Follow-Up						Follow-Up							Provider Focus Group & Client Interview	
LGUD (n=6)	Base					Pre	finCAT			Post	Champion Follow-Up						Follow-Up								Provider Focus Group & Client Interview

**Data Analysis**

For this analysis, primary variables are CIRS, GAS, and LPS scores. Secondary variables are the EBPAS and additional qualitative measures of care provider attitudes.

The data analysis is as follows: (1) A descriptive profile of demographic and baseline data will be developed; (2) We will develop a descriptive profile of session attendance; (3) We will compare pre/post/follow-up measures within treatment groups using ANOVA with posthoc analyses to determine change between time points. Cohen’s d will be used to assess effect size. For all analyses  $p < .05$  will be used as the level of significance.

Transcripts from focus groups and individual interviews will be thematically analyzed using a content analysis strategy as articulated by Hsieh & Shannon, 2005. The analysis will be validated through the use of 2 independent coders and full team reviews of code summaries.

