### ***The Proposed Project***

The proposed project will expand our knowledge of the role of compensatory cognitive interventions for forensic inpatient populations with schizophrenia. Over the course of 6 months, we will conduct a feasibility study of the delivery of a modified forensic inpatient version of Cognitive Adaptation Training. The objective of this single group study with pre-post and follow up assessments is to determine if preliminary outcomes and follow up findings support the feasibility of a modified version CAT within a forensic inpatient setting. Feasibility data will be used to inform (i) any necessary adjustments to the intervention, (ii) any necessary adjustments to the optimal time of study for outcomes to be observed, and (iii) to inform future trials with respect to anticipated recruitment and drop-out rates and optimal powering.

This study would be among the few examinations of CAT as an inpatient intervention to date, as well as the first to examine a modified cognitive adaptation training approach in both a North American and forensic inpatient setting, and would make a substantial contribution to the evidence-based intervention literature. This intervention will be referred to as forensic inpatient CAT or finCAT.

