### ***The questions for this project are:***

#### **(1) Is finCAT feasible for forensic inpatient populations with a schizophrenia spectrum diagnosis?**

Based on preliminary work we hypothesize that finCAT will prove acceptable to patients and inpatient staff and will demonstrate positive outcomes with respect to functioning and inpatient room organization.

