**And**

## **(2) What are the attitudes of inpatient forensic occupational therapists and clinical teams towards implementing finCAT on their units?**

### **Methods**

#### ***Study Design Overview***

This study will expand on our preliminary work at CAMH. The study will be implemented on four CAMH general security forensic inpatient units. There will be four weeks of CAT Clinician--delivered treatment focusing on two goal areas – room organization and personal hygiene, followed by two months of maintenance by CAT Unit Champions with pre, post, and two-month follow-up, as well as project-end evaluations. In the first four weeks, we will conduct a trial of finCAT for two of the four inpatient general forensic units, followed by two months of finCAT maintenance with Unit CAT Champions supported by the CAT Clinician. This process would then be repeated on the remaining two general units at CAMH. Previous implementation of CAT has demonstrated gains within one-month; however, follow-up assessments were not conducted to determine if gains were maintained over time. While brief, this time period (i) reflects the intent of this study as a pilot test of feasibility and, (ii) aligns with this circumscribed version of CAT (as compared to the more comprehensive community version with broader outcome domains). Data will be collected from both primary participants (inpatients) and the clinical team.

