### **Measures**

#### *Clutter Image Rating Scale (CIRS)*

Room organization will be measured by ratings on the Clutter Image Rating Scale (CIRS; Frost et al., 2008). The CIRS is a 9-picture visual analogue scale used to quantify and standardize the amount of clutter in 3 different living spaces (kitchen, living room, and bedroom). For this project, only the bedroom rating scale will be utilized. The CIRS is used to measure the severity of clutter in compulsive hoarding. It has been shown to be less affected by an over-reporting bias and to have strong inter-observer reliability with a strong participant/experimenter correlation. Before and after photos will be taken of each participant's room. These photos will be rated by 2 blinded student investigators with the mean rating taken.

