#### *Life Skills Profile (LSP)*

Personal hygiene will be measured by scores on the Life Skills Profile (LSP; Rosen, Hadzi-Pavlovic, & Parker, 1989). The LSP consists of 39 clinician-rated questions on a four-point scale and measures various aspects related to daily life activities: self-care; non-turbulence; social contact; communication; responsibility. For this project, only the self-care ratings from the full LSP-39 will be completed by service providers. Current inpatient research on the use of CAT also uses this scale as a primary measure of the effectiveness of CAT. Scores will be obtained from the nursing staff not directly involved in the delivery of the finCAT intervention.

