#### *Goal Attainment Scaling (GAS)*

Goal Attainment Scaling (GAS) will be employed as a sensitive measure of progress on individually defined goals. GAS has demonstrated good reliability and validity with severe mental illness populations (Hurn et al., 2006). Goal attainment scaling involves the setting of 3-5 goals, each operationalized on a 3-point scale. Goals are individualized to the client and assessment of progress is determined through consensus of the clinician and case manager.

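### Do three primary variables, each tested at p<.05 with no stated rule for combining them, leave the feasibility conclusion open?

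*Combined protocol and SAP*

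**What the plan says.** The Proposed Project gives the objective of this single-group study: it "is to determine if preliminary outcomes and follow up findings support the feasibility" of the modified intervention. The same paragraph lists what the feasibility data are for: adjusting the intervention, adjusting the length of study, and informing recruitment, drop-out and powering in later trials. The first study question hypothesises that finCAT will be acceptable to patients and staff and "will demonstrate positive outcomes with respect to functioning and inpatient room organization". Study Design Overview names the two goal areas, "room organization and personal hygiene, followed by two months of maintenance".

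The measures have different raters. CIRS room photographs are "rated by 2 blinded student investigators with the mean rating taken". LSP self-care scores come from "nursing staff not directly involved in the delivery of the finCAT intervention". For GAS, "assessment of progress is determined through consensus of the clinician and case manager", and nothing is said about independence from delivery.

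Data Analysis says that "primary variables are CIRS, GAS, and LPS scores" (LPS is evidently the LSP). The measures are compared across pre, post and follow-up "within treatment groups using ANOVA with posthoc analyses to determine change between time points", with Cohen's d for effect size and p<.05 throughout. The same section plans profiles of baseline data and session attendance, and a content analysis of focus groups and interviews. Participants says that no data were available for a formal power analysis and that the sample of 24 has to be regarded as underpowered.

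**The concern.** Outcomes feed a judgement about feasibility, and three of them are called primary, yet nothing says how to read them together. If rooms become tidier and hygiene does not, the same data could be reported as supporting the hypothesis or as failing to support it. The mapping is also incomplete. CIRS plainly measures room organization. LSP self-care is described as measuring personal hygiene, so treating it as functioning is an inference. GAS covers individual goals that the text ties to neither hypothesised domain. GAS is also the one measure whose raters are not said to be separate from delivery, so a change on GAS alone could carry a favourable conclusion. What would be at stake is a conclusion settled after the results are known, more than an inflated error rate.

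The reference to treatment groups in a single-group study adds a smaller doubt about what is being compared.

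**Working it through.** **Inputs from the documents.** Four units of 6 give 4 × 6 = 24, which reproduces the stated sample size. There are three primary variables, three time points in the ANOVA, and a level of .05. The plan gives no power, SD, correlation or numerical effect size, so there is no power figure to reproduce.

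**Assumptions.** Two-sided tests; one group of 24 with no loss and no clustering by unit; continuous normal scores; correlation between time points 0.5; follow-up mean equal to post mean; correlation between variables 0 to 0.8. Effects are in SDs of change.

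**One variable.** The critical value is t(.975, 23) = 2.069 and the noncentrality is d√24. At d = 0.60 this is 0.60 × 4.899 = 2.94, giving power 0.804. At d = 0.50 power is 0.650. Power of 80% is reached at d = 0.597, so the plan's claim that the sample suits medium-large effects is plausible for a single variable. The 95% CI half-width for a mean change is 2.069/√24 = 0.42.

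**Three variables, paired pre-post tests.** The closed forms hold at correlation 0. The ranges are from simulation over correlations 0 to 0.8, 40,000 runs per cell.

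| Truth | Reading | Correlation 0 | Range |
|---|---|---|---|
| CIRS only, 0.60 | any one improves | 1 − 0.196 × 0.975² = 0.814 | 80–81% |
| CIRS only, 0.60 | CIRS and LSP both | 0.804 × 0.025 = 0.020 | 2.0–2.5% |
| GAS only, 0.60 | CIRS and LSP both | 0.025² = 0.0006 | at most 1.1% |
| All three, 0.60 | any one improves | 1 − 0.196³ = 0.992 | 90–99% |
| All three, 0.60 | CIRS and LSP both | 0.804² = 0.646 | 65–73% |
| All three, 0.60 | all three | 0.804³ = 0.520 | 52–69% |
| No change | any one improves | 1 − 0.975³ = 0.073 | 5–7% |
| No change | any omnibus F significant | 1 − 0.95³ = 0.143 | 10–14% |

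**Closer to the written analysis.** Data Analysis specifies ANOVA followed by post hoc tests. If the pre-post contrast is read only after a significant repeated-measures ANOVA:

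- No true change: any false improvement falls to about 3–4%.
- One variable: power is 76–77% at 0.60 and 58–59% at 0.50.
- CIRS and LSP both required: 59–68% at 0.60 and 34–48% at 0.50.

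The post hoc method is not named, and a stricter one would lower these figures further.

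**What stricter handling would cost.** Bonferroni across the three variables (0.05/3 = 0.0167) would raise the effect detectable with 80% power from 0.60 to 0.70. A both-domains rule would lower the chance of a positive reading from 76–77% for one variable to 59–68% at 0.60. It would also demote GAS, which the plan makes primary, and settle the meaning of functioning in a way the documents do not.

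**The case for a change.** The strongest case for a change is that it would be cheap and that the gap is real. The plan uses the word primary, sets a significance level and links outcomes to the objective, so calling the study a pilot does not by itself dispose of the matter. With the same underlying truth, a positive reading could be about 80% or about 2% likely under two rules that the text does not exclude. One sentence declaring the tests exploratory would need no patients, visits or alpha.

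Part of this stands: the text has no combining rule, and the figures reproduce. But the contrast compares two rules that a reader has to supply. The any-one rule is not in the plan. The hypothesis joins functioning and room organization, which reads more naturally as both. Declaring the tests exploratory would stop a claim built on a single p-value, yet it would not say what mixed results mean, so the supposed harm would remain. A both-domains rule would settle that, at the price shown above. The simulated model also suits these scales only roughly: GAS uses 3 to 5 goals on 3-point scales and CIRS a 9-picture rating, so the GAS-only case is the least secure.

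**Conclusion.** No change to the plan is needed. The missing combining rule is a detail that analysts of a 24-person single-group pilot fill sensibly: report all three named variables whatever their direction, with changes, effect sizes and intervals, state who rated each, and weigh them alongside acceptability, attendance and the qualitative findings. None of the listed uses of the feasibility data turns on a significant p-value. Because the three variables are named in advance, leaving one out of the report would be visible.

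False-positive inflation is modest: about 3–4% for any false improvement under ANOVA with post hoc tests, or 5–7% for paired tests alone, against a nominal 2.5% in that direction for one variable. A formal rule is a trade-off between a firmer reading and lower power in a study that already calls itself underpowered. LPS for LSP, and treatment groups in a single-group study, are clerical slips that the rest of the document resolves.

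The sizes rest on the assumed correlations, effects and normal scores. The conclusion rests on the stated purpose of the study. It would change if the study were to be reported as a confirmatory test of efficacy.

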#### ***Participants***

Participants will be enrolled from four CAMH forensic inpatient units (medium security excluded). A total of 6 participants will be recruited from each unit for a total of 24 participants. Attrition is expected to be minimal given the inpatient context and previous delivery of CAT with this population. While previous data are not available for formal power analysis, this sample size is anticipated to prove adequate for the detection of medium-large effects though must be considered underpowered and will inform future power analysis.

Specific criteria include:

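### The only planned effect size is a single-group pre-post Cohen's d, in a study meant to inform the powering of later trials. Taken at face value it could undersize a controlled trial, and the untreated interval on the delayed units goes unused.

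*Combined protocol and SAP*

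**What the plan says.** The Proposed Project section describes the design: "The objective of this single group study with pre-post and follow up assessments". Among the uses of the data it lists is "to inform future trials with respect to anticipated recruitment and drop-out rates and optimal powering".

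The Participants section sets the size: "A total of 6 participants will be recruited from each unit for a total of 24 participants". It gives no calculation: "While previous data are not available for formal power analysis, this sample size is anticipated to prove adequate for the detection of medium-large effects". It adds that the sample "must be considered underpowered and will inform future power analysis".

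The Data Analysis section gives the whole quantitative comparison in one sentence: "We will compare pre/post/follow-up measures within treatment groups using ANOVA with posthoc analyses to determine change between time points". The next sentence says that Cohen's d "will be used to assess effect size". It does not say whether the mean change is divided by the Pre-CAT SD, a pooled SD or the SD of change, and it asks for no confidence interval. No other effect-size statistic is named.

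Table 3 schedules CIRS and LSP at both Baseline and Pre-CAT; GAS starts at Pre-CAT. In the Study Overview table, as it reads in the extracted text, all four units have Baseline at week 0. Two units have Pre at week 1 and Post at week 6. The other two have Pre at about week 5, before any finCAT. The Data Analysis section makes no use of the Baseline-to-Pre change and does not compare waiting units with treated ones.

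**The concern.** A d from one group measured before and after treatment is not an estimate of a treatment effect against control. It adds to that effect any change that would have occurred anyway: regression to the mean, extra staff attention, ward or seasonal drift, and rater expectation where raters know what was delivered.

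The protocol leaves room for these. Under Recruitment, clinical staff approach the patients they consider appropriate, so some regression to the mean is possible. GAS, a primary variable, is scored by agreement between the clinician and the case manager. LSP is scored by nurses who do not deliver finCAT, but their teams are taught CAT and told of clients' goals and strategies.

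Informing the power of later work is one of the study's stated purposes. If a later two-arm trial took this d as its between-group difference, any non-specific share would be counted as treatment effect and the trial would be sized for a difference that is too large. With 24 participants the point estimate is also too imprecise to carry that weight alone. Meanwhile the one untreated comparison period in the design is collected and left unanalysed.

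**Working it through.** **Inputs from the documents.** 4 units × 6 = 24 participants, which reproduces the stated total. Two early units and two delayed units give 2 × 6 = 12 in each set. The significance level is .05.

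**Assumptions, because the documents give no figures.** Two-sided tests, 80% power, a later trial with two equal parallel arms, an illustrative observed d of 0.5, and non-specific shares of 20%, 30% and 50%.

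**1. Precision of d at n = 24.** Write d_z for mean change divided by the SD of change. Then t = d_z × √n = 0.50 × √24 = 2.45 on 23 df. Inverting the noncentral t distribution and dividing by √24 gives a 95% interval of 0.07 to 0.92. For d_z = 0.60 the interval is 0.16 to 1.03. Read as a between-group d, 0.60 asks for 45 per arm, but its limits of 0.16 and 1.03 ask for 624 and 16 per arm.

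**2. Effect of non-specific change.** Suppose the observed d is 0.5, already on the between-group scale, and a share s of it is not due to finCAT. The true effect is 0.5 × (1 − s). A trial planned on 0.5 has 64 per arm (two-sample t test, 80% power).

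| Share s (assumed) | True d | Power with 64 per arm | Per arm needed for 80% |
|---|---|---|---|
| 0% | 0.50 | 80% | 64 |
| 20% | 0.40 | 61% | 100 |
| 30% | 0.35 | 50% | 130 |
| 50% | 0.25 | 29% | 253 |

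**3. The unused contrast.** As the Study Overview table reads:

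- Early units, Pre to Post: week 1 to week 6, treated, 12 participants.
- Delayed units, Baseline to Pre: week 0 to about week 5, untreated, 12 participants.

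Both intervals last about five weeks and overlap for about four. CIRS and LSP are measured at all four of these points; GAS is not, since it has no Baseline.

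**4. What that contrast can deliver.** With 12 against 12, a two-sample t test has 80% power only for d of about 1.2. In units of the SD of change, the 95% half-width is about 2.07 × √(2/12) = 0.85. Both figures ignore clustering by unit, which would make them worse.

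**The case against.** **The documents never name d as the power input.** This stands. They say the study will inform powering and that it "will inform future power analysis"; they do not say which statistic will be used. SDs, correlations and retention could serve, and nothing rules them out. A reader might infer that d is the intended input because it is the only effect size named. That is an inference, so the risk is conditional on d being used that way.

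**The missing denominator need not undersize a later trial.** This also stands. A reader might reason that d_z exceeds a raw-score d, by the factor 1/√(2(1 − r)), where r is the pre-post correlation, and so must lead to too small a trial. That needs r above .5 and a later analysis of post scores that ignores baseline. For a raw-score d of 0.5, planning on d_z at r = .7 gives 39 per arm. Power is then 59% for a post-score comparison, but 80% for change scores and 86% with baseline adjustment. At r = .3 it gives 89 per arm, more than the 64 needed. The direction is therefore open, and these figures do not measure the problem.

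**The protocol has safeguards.** CIRS photographs are rated by two blinded students, and LSP raters do not deliver finCAT. No score threshold is set for entry, so regression to the mean is possible but not established. This narrows the rater-expectation argument, chiefly to GAS and in part to LSP. It does not remove change over time or change from added attention.

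**Low power is already disclosed.** True, but admitting that a sample is underpowered is not the same as reporting an interval or saying how the estimate may be used.

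**The early-versus-delayed contrast is weak.** Agreed. It sets two units against two, no randomisation of units is described, and GAS is excluded. A reader might be tempted to treat it as the controlled estimate on which to power the next trial; the design does not support that.

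**Conclusion.** The concern holds as a conditional one. The planned analysis yields only an uncontrolled d, undefined and without an interval, in a study meant to inform powering. Using its point estimate as a between-group effect could undersize a controlled trial. The main ground is non-specific change: with the assumed shares of 20% to 50%, power falls from 80% to between 61% and 29%. The actual share cannot be known from the documents, and if it were zero this loss would vanish. Imprecision at n = 24 adds to the risk in either direction. The documents do not support the claim that later trials would necessarily be too small.

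The clearest improvement open to the sponsor is the unused untreated interval. It would give a concurrent check on how much CIRS and LSP move without finCAT, though only a rough one. The change is worth making, but it does not threaten the feasibility aims.

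**What to change.** In the Data Analysis section:

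1. Add, for CIRS and LSP, a comparison of the early units' Pre-to-Post change with the delayed units' Baseline-to-Pre change, with a 95% confidence interval. Label it descriptive: 12 against 12, two units against two, no randomisation described, not available for GAS. Confirm the week numbers against the original Study Overview table first.
2. For each primary variable, report mean change, the SDs at each time point and of change, the pre-post correlation, and d with its denominator named and a 95% confidence interval. The choice of denominator matters less than stating it. GAS may need its own, since scores may vary little at Pre-CAT.
3. State that the single-group d alone will not be taken as the between-group effect when a later trial is powered.

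The cost is one small and imprecise extra analysis plus some reporting text. No new data, visits or participants are needed.
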